## 4.1.3 IMP groups comparison

# 4.1.3.1 Main Inferential model

Unless otherwise specified, all the endpoints referred in detail in the following section will be analyzed according the same statistical model allowing a comparison of results between the studied endpoints. The significance of the difference between the IMP compared with placebo will be assessed through a general model of analysis of Covariance (ANCOVA) in which the studied endpoint at final time (noted Yf) constitutes the dependent variable of the model. Independent variables are (1) the baseline value of the studied endpoint (noted Yb) analyzed as a fixed covariate, (2) the treatment effect (Noted Trt) coded 0 (placebo) or 1 (IMP) (cell mean contrast formulation), and (3) the center considered as a random factor of the intercept constituted by a fixed part  $k_0$  and a random component N(0, $\sigma_c$ ). This model is summarized by the following expression:

 $Y_{if} = (k_0 + \zeta) + k_b Y_b + k_t Trt + \epsilon_i \quad \epsilon_i = N(0, \sigma) \text{ and } \zeta = N(0, \sigma_c) \text{ [general Model -1]}$ 

Note 1-This model does not assume a treatment-baseline interaction term (as required in CPMP, 2003). Our decision of using center as a random factor is justified by the useless estimate of each center, in focusing on the measurement of the standard deviation of the intercept. The treatment will be considered as fixed factor without center random component.

Note 2- This model is a Linear Mixed Model (LMM) as it combines random and fixed factors, assumes linearity of baseline and hypothesizes the studied endpoint distributed according to a normal (Gaussian) distribution. This model constitutes the main model used in this trial for all the studied endpoints unless otherwise specified.

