4.5.2. Investigational treatment allocation

When the patient receives his/her study number, the corresponding investigational treatment identified by the treatment number will be allocated to the patient according to the randomization list established by an independent company and managed by Interactive Web Response Services (**IWRS**) according to randomization.

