# 4.1.3.2 Multiple Testing

# (ICH E3; 9.7.1, 11.4.2.5. ICH E9; 2.2.5, FDA-2017)

The main analysis is defined as the analysis of covariance following general Model 1 [section 4.1.3.1] conducted on the main selection (FAS), on the primary endpoint (UNS) considered as a global endpoint aggregating both EDS and cataplexy symptoms. Secondary endpoints will be PDSS and the UNS-CTP subscale measuring the IMP effect on EDS and cataplexy, respectively. Two other secondary endpoints will be the weekly rate of cataplexy measured by the patient diary (WRC) and the MWT. All the other endpoints will be considered as exploratory and supportive.

The main endpoint (UNS) and the four secondary endpoints necessitate 5 tests. We will use the fixedsequence strategy testing the endpoints in the pre-defined order UNS, PDSS, UNS-CTP, WRC and MWT, each one tested at two-sided  $\alpha$ =.05 significance, moving to the following endpoint conditionally to a significant difference reached on the previous endpoints (FDA, section C.5). This strategy protects the results with type 1 risk bounded by P=.05.

Our choice is justified as follows: UNS constitutes a global appraisal of both EDS and cataplexy in pediatric narcolepsy and must regarded as a relevant general first endpoint. PDSS and UNS-CTP are validated scales to measure EDS alone and cataplexy alone, respectively. Conditionally to a significant effect on the main UNS endpoints, the effect of the IMP will be assessed on the two symptoms, separately. Finally MWT and WRC are alternative endpoints to measure EDS and cataplexy, respectively, and will be assessed conditionally to the significance obtained on UNS, PDSS and UNS-

CTP. Besides, EDS is a more frequent symptom, thus it was tested before cataplexy, and PDSS and UNS-CTP were shown with a higher power than MWT and WRC, respectively [ref-validation]

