# 4.2 Sample size calculation

(ICH E3; 9.7.2. ICH E9; 3.5)

The initial protocol was based in assuming a Pearson correlation coefficient of R=0.5 between prebaseline and final values of PDSS, two pre-baseline measurements [(V1+V2)/2] and two post-baseline measurements [(V6+V7)/2]. A standardized mean difference of at least 0.5 (considered as the minimum clinically significant difference) will be detected at a two-sided 0.05 confidence level with a power of at least 0.8, when the sample size/group is at least 20 and 40 patients for control and tested drug groups, respectively.

At a later stage, UNS measuring EDS and cataplexy was used as the primary outcome instead of the PDSS. As UNS was expected with a residual variability larger than PDSS, the initial power of .75 judged as too small, a recalculation of the sample size was performed on a standardized mean difference of 0.5 on the UNS (considered as the minimum clinically significant difference), a ratio 1:2, and a correlation R=0.4. Under these assumptions, and ANCOVA test at 0.05 two-sided confidence level, the probability of a significant effect will be found with a power of 0.85 when the sample size exceeds 36+72 patients for control and tested drug groups, respectively, thus a total of 108 patients.

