# Safety Set (SAF):

All patients who receiving at least one treatment dose.

4 subgroups will be used in some analyses, according to:

- Age at baseline ([6-11], [12-18[)
- Sex
- BMI at baseline (underweight , normal, overweight and obese)
- Type of narcolepsy (Type 1 or Type 2)

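### The primary UNS ANCOVA omits narcolepsy type, a plausibly prognostic variable known at entry; the cost is some precision, not validity

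*SAP*

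**What the plan says.** **Model.** SAP 4.1.3.2: "The main analysis is defined as the analysis of covariance following general Model 1", on the FAS, for the UNS total. SAP 4.1.3.1 gives that model three terms: "Independent variables are (1) the baseline value of the studied endpoint", treatment, and "the center considered as a random factor of the intercept". Protocol 7.4 likewise names only baseline adjustment and centre heterogeneity.

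**Scale.** Under SAP 4.1.5.5 the UNS has four cataplexy items and seven sleepiness items, each scored 0 to 4. The total runs from 0 to 44.

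**Narcolepsy type.** Inclusion criterion 1 (protocol 3.4.1) requires an ICSD-3 diagnosis of type 1 or type 2. SAP 4.3 lists "Type of narcolepsy (Type 1 or Type 2") among four subgroups. SAP 4.5.3.2.2 and 4.5.3.2.3 restrict the UNS cataplexy subscore and the weekly cataplexy rate to type 1. For the UNS total, SAP 4.5.3.1.2 uses subgroups for descriptive statistics only, and the one covariate added in a sensitivity analysis is sodium oxybate with its interaction.

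**Imputation and allocation.** SAP 4.1.4.1 imputes from age, gender and the main model's terms. Protocol 4.5.2 allocates treatment "according to the randomization list established by an independent company" and describes no stratification by type.

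**Sample size.** SAP 4.2 assumes a standardised difference of 0.5, a 1:2 ratio "and a correlation R=0.4", and an "ANCOVA test at 0.05 two-sided confidence level". It states that "the probability of a significant effect will be found with a power of 0.85 when the sample size exceeds 36+72 patients".

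**The concern.** A covariate that predicts the outcome, is fixed before randomisation and is already collected usually belongs in the model. Type is a natural candidate. The SAP's own restriction of the cataplexy endpoints to type 1 implies that type 2 children score at or near zero on four of the eleven items and so have little room to improve there. Two children with the same baseline total but different types may then have different expected final totals.

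At stake is the width of the confidence interval for the primary comparison. The UNS test also opens the fixed testing sequence (SAP 4.1.3.2), so precision lost on it is felt by the four secondary endpoints behind it.

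**Working it through.** **1. Cataplexy share of the scale.** 4 items × 4 points = 16; 16/44 = 36%.

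**2. The plan's power.** Inputs from SAP 4.2: difference 0.5 SD, R = 0.4, 36+72 patients, two-sided 0.05. R is taken as the correlation between the baseline mean and the final mean.

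- Residual variance: 1 − 0.4² = 0.84
- 1/36 + 1/72 = 1/24
- SE = √(0.84/24) = 0.187 SD; 0.5/0.187 = 2.67
- Power: 0.754 (noncentral t, 105 df) or 0.762 (normal approximation)

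The stated 0.85 does not reproduce this way. A one-sided 0.05 test gives 0.848. Reading R as a single-visit correlation with two visits before and two after gives 0.946 two-sided. That discrepancy is a separate matter; here 0.754 is only the starting level.

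**3. Effect of adding type.** If type explains a share q of the residual variance after baseline, SE = √(0.84(1 − q)/24). The documents give no q, so a range is shown (noncentral t, 104 df once type is added):

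| q (assumed) | Power |
|---|---|
| 0 (type not in model) | 0.754 |
| 0.05 | 0.775 |
| 0.10 | 0.797 |
| 0.14 | 0.815 |

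**4. What q is plausible?** The protocol synopsis equates the target with 3 UNS points, so 0.5 SD implies SD = 6. Assume the same SD at baseline and end, a type effect of D points at both times, and no treatment-by-type interaction. Take the type 1 share p from one-third to 80%. These are the shares with cataplexy given in SAP section 3 and in the protocol introduction, used as proxies for type 1.

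- Variance due to type: b = p(1 − p)D²
- Within-type correlation: r = (14.4 − b)/(36 − b), where 14.4 = 0.4 × 36
- Residual variance with type: (36 − b)(1 − r²), against 36 × 0.84 = 30.24 without

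Low end, p = 0.8 and D = 2: b = 0.64, r = 0.389, residual 30.0, ratio 0.992, so q is about 1%.

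High end, p = 0.5 and D = 6: b = 9, r = 5.4/27 = 0.20, residual 27 × 0.96 = 25.92, ratio 0.857, so q is about 14%. Power is then 0.816 (0.823 by the normal approximation).

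At D = 8 the gain would be larger (normal-approximation power 0.835 to 0.883). That sits close to what R = 0.4 allows: it is infeasible at p = 0.5, and the within-type correlation falls to 0.04 or less at p = 0.7 and p = one-third.

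**5. What chance imbalance could do.** With equal SDs the baseline slope is 0.4, so baseline adjustment removes about 40% of a persisting type difference. The remainder is 0.6D, or 1.2 to 3.6 points for D = 2 to 6. The between-arm difference in type share has SD √(p(1 − p)/24) = 0.08 to 0.10. A typical imbalance therefore moves the estimate by 1.2 × 0.08 = 0.10 to 3.6 × 0.10 = 0.36 points. The standard error of the treatment effect is 6 × 0.187 = 1.12 points.

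**The case against.** The strongest reply is that nothing is broken. A randomised comparison that leaves out a prognostic variable keeps its type I error, and the variation due to type is already in the residual variance and the confidence interval. The model in the SAP matches protocol 7.4. The SAP also prefers one common model so that endpoints can be compared. All of that stands, and it limits the point to precision.

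Four stronger readings are tempting, and the documents do not support them.

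- *Type imbalance is likely and goes uncorrected.* By the hypergeometric distribution, a difference of 10 percentage points or more has a probability of about 20% to 31% for type 1 shares from one-third to 80%. That is not rare, but not the expected outcome. Baseline UNS contains the cataplexy items and absorbs part of it.
- *R = 0.4 shows that baseline leaves a large type effect behind.* It does not. Type is a stable trait; a large shared effect would push R up, so a low R caps how large that effect can be.
- *Type decides whether 16 points can change.* All eleven items are scored in everyone. A child at zero cannot improve on an item but can worsen. The documents report no UNS data by type.
- *The same change is needed for PDSS and MWT.* The cataplexy-item argument does not reach a sleepiness scale or a sleep-latency test, and MWT is analysed by Cox regression (SAP 4.5.3.2.4), not by this model.

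**Conclusion.** The point holds as an optional gain in precision for the UNS total. Type is available at entry and plausibly prognostic, and it is missing from both the primary model and its sensitivity analyses. Under the assumptions in the working, it would remove between nothing and about 14% of the residual variance. Power would rise from about 0.75 to at most about 0.82; a gain near zero is equally compatible with the documents. The figures rest on an assumed type effect of up to 6 points, an implied SD of 6, equal variances at baseline and end, and R applying to the visit means.

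A reader might infer that the primary result would be biased without this term, or that adding it would restore the planned power of 0.85. Neither follows. On the two-sided reading used here, type would have to explain about 20% of the residual variance to reach 0.85 at 108 patients.

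**What to change.** Before unblinding:

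1. Add narcolepsy type (1/2) as a fixed covariate in general Model 1 for the UNS total only.
2. Name type explicitly in the UNS imputation model. SAP 4.1.4.1 describes that model twice, once by reference to the main model's terms and once as age, gender and baseline score, so the change would not carry through both descriptions by itself.
3. Record the change and its reason in SAP 4.6, which now reads as not applicable, because protocol 7.4 describes baseline and centre only.

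No new data are needed. The cost is about 1 of 105 degrees of freedom and a documented departure from the single common model. If the sponsor prefers to leave the primary model untouched, a pre-specified sensitivity analysis with type, beside the sodium oxybate one, is a lesser alternative: it would show robustness but add no precision to the primary test.

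A main effect for type does not test whether the treatment effect differs by type. That would need an interaction term or estimated subgroup effects, whereas the SAP plans only descriptive subgroup statistics for the UNS total.

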# 4.1.3.2 Multiple Testing

# (ICH E3; 9.7.1, 11.4.2.5. ICH E9; 2.2.5, FDA-2017)

The main analysis is defined as the analysis of covariance following general Model 1 [section 4.1.3.1] conducted on the main selection (FAS), on the primary endpoint (UNS) considered as a global endpoint aggregating both EDS and cataplexy symptoms. Secondary endpoints will be PDSS and the UNS-CTP subscale measuring the IMP effect on EDS and cataplexy, respectively. Two other secondary endpoints will be the weekly rate of cataplexy measured by the patient diary (WRC) and the MWT. All the other endpoints will be considered as exploratory and supportive.

The main endpoint (UNS) and the four secondary endpoints necessitate 5 tests. We will use the fixedsequence strategy testing the endpoints in the pre-defined order UNS, PDSS, UNS-CTP, WRC and MWT, each one tested at two-sided  $\alpha$ =.05 significance, moving to the following endpoint conditionally to a significant difference reached on the previous endpoints (FDA, section C.5). This strategy protects the results with type 1 risk bounded by P=.05.

Our choice is justified as follows: UNS constitutes a global appraisal of both EDS and cataplexy in pediatric narcolepsy and must regarded as a relevant general first endpoint. PDSS and UNS-CTP are validated scales to measure EDS alone and cataplexy alone, respectively. Conditionally to a significant effect on the main UNS endpoints, the effect of the IMP will be assessed on the two symptoms, separately. Finally MWT and WRC are alternative endpoints to measure EDS and cataplexy, respectively, and will be assessed conditionally to the significance obtained on UNS, PDSS and UNS-

CTP. Besides, EDS is a more frequent symptom, thus it was tested before cataplexy, and PDSS and UNS-CTP were shown with a higher power than MWT and WRC, respectively [ref-validation]

#### 4.1.4 Missing data

#### 4.1.4.1 General considerations

(ICH E3; 9.7.1, 11.4.2.2. ICH E9; 5.3. EMA Guideline on Missing Data in Confirmatory Clinical Trials) Missing data will be imputed for five main endpoints of this study (UNS, PDSS, UNS-CTP, WRC and MWT). For the other endpoints no missing value will be imputed.

A Multiple Imputation (MI) procedure will be used to impute the missing evaluations, as a prior step, assuming that those patients would be in their randomized arm. The partially complete datasets will be generated with a model including the following covariates age, gender and the main model components (section 2.2).

A total of 100 imputed partially complete datasets will be generated.

MI inference involves 3 consecutives phases:

- 1/ Imputation step:

The missing pattern is supposed to be monotone, so the regression method will be used to impute missing data.

The partially complete datasets will be generated with a model including age, gender factors and taking into account the baseline score of the primary endpoint, based on patient which every postbaseline measurement available. It is of note that this imputation step might be preceded by one MI approach based on MCMC method, in case of arbitrary missing pattern. A total of 100 imputed partially-complete datasets will be generated.

The mean MD imputation will based on Missing at Random (MAR) corresponding to the hypothesis that missingness is assumed independent of the outcome, or to estimate a "de jure" (per protocol) estimand, censoring after any protocol deviation. This hypothesis was considered as the most likely in this particular context.

Despite the likelihood of this option, a secondary MD imputation will be conducted according to the Missing at Random hypothesis (MNAR), for which several options to construct the joint distribution of the observed and unobserved data have been proposed, each reflecting a different MNAR mechanism (Carpenter et al., 2013). This appropriate choice was discussed in the general context of narcolepsy. We assumed that after dropping out, participants from the active arm have the same outcomes as the reference group individuals, hypothesizing that the treatment effect is lost after the individual leaves the study. This option is called Jump to reference (J2R), after dropout, the participant's conditional outcomes are associated to those of the control arm. The joint distribution is a Multivariate Normal model with mean parameters from the randomised arm until date of interruption (Di) and from the reference group afterward. The covariance matrix corresponds to the parameters from the randomised arm until Di and to the reference group for the conditional components of the post-dropout variables, given the pre-dropout measurements.

Concerning the J2R, the jump-to-placebo approach will be set up for these patients' imputations, by using the %mistep macro from James Roger (https://www.lshtm.ac.uk/research/centres-projects-groups/missing-data#dia-missing-data, zip file MISTEP20180327).

Usualy, a sequence of %mistep is run, the subsequent models include the residuals of the previous model. In this study only one model will be used (for the endpoint value imputation).

In case of imputed data outside the range, the minimun or the maximun bound will be used.

This macro will be used because no SAS procedure are currently available to perform the jump to reference approach.

- 2/ Analysis step:

The same analysis as described above will be applied to each of the 100 imputed datasets.

- 3/Combination step:

Statistical inferences will be generated by combining results from 100 analyses using Rubin's formulae (Rubin, 1987).

The multiple imputation estimator of the difference between active treatment and placebo is the average of the individual 100 estimators. The variance of the estimator is the combination of the between and within-imputation variability (Kenward & Carpenter, 2007).

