# 4.1.5 Derived variables

## 4.1.5.1 General definitions

The following definitions will be considered:

- Analysable value will be defined as any non-missing value.
- Baseline value will be defined as :
  - For UNS, PDSS and CASS parameters as the mean of V1 and V2 values on condition that values are prior to the first IMP intake (*i.e.* before or the same date as the first IMP intake date). In case of a visit missing value, the baseline will be equal to the non-missing value.
  - For other parameters, the last analysable value prior to the first IMP intake (*i.e.* before or the same date as the first IMP intake date).

Note: In case of patient randomised but not treated over the blind period: value at baseline is defined as the last analysable value prior or equal to the date of randomisation.

- Post-baseline value will be defined as any value recorded at a given timepoint after baseline.
- Change from baseline will be defined as the arithmetic difference between a post-baseline value and the baseline value for a given variable at a given time point.
- End value will be defined only for UNS, PDSS and CASS parameters as :

- The mean of V6 and V7 values. In case of a visit missing value, the End value will be equal to the non-missing value.

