## 4.5.3.1.2 Sensitivity and other analyses

Sensitivity analyses will be performed to assess the robustness of the primary analysis results:

- Using MNAR option of the MI imputation (removing the treatment effect in the imputation model of the partially-complete data sets).
- Using the same model as for the primary analysis will be performed with the center as fixed effect instead of random effect.
- Using the same model as for the primary analysis will be performed with in addition the oxybate sodium intake and treatment-by- oxybate sodium intake interaction as fixed effects.
- Using an observed Cases analysis: The same model as for the primary analysis will be performed in patients having a value of UNS total score at V6 or V7 (i.e. in this case analysis restricted to completers the double blind period).
- Using the same model as for the primary analysis will be performed by actual treatment group, only if actual group is different from randomized group.

The same statistical elements to estimate the treatment effect as for primary analysis will be provided.

In addition, value and change from baseline descriptive statistics at each visit by treatment group will be provided, overall and by subgroups.

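### SAP 4.1.4.1 words the primary UNS imputation model in two ways, one without treatment, and the linked rules on MNAR, prohibited medication and protocol changes do not agree

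*SAP*

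**What the plan says.** The primary analysis is multiple imputation under MAR followed by the mixed ANCOVA of SAP 4.1.3.1, whose terms are baseline, treatment and a random centre.

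SAP 4.1.4.1 gives the imputation model twice:

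- **List A** (opening paragraph): "a model including the following covariates age, gender and the main model components (section 2.2". SAP section 2 is the introduction and has no subsections, so the reference fails. The intended place is evidently 4.1.3.1.
- **List B** (imputation step): "a model including age, gender factors and taking into account the baseline score of the primary endpoint", continuing "based on patient which every postbaseline measurement available". Neither treatment nor centre appears.

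On the MNAR option, 4.1.4.1 defines J2R and adds: "In this study only one model will be used (for the endpoint value imputation". Section 4.5.3.1.2 describes the same option as "removing the treatment effect in the imputation model of the partially-complete data sets".

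On which values count, 4.1.5.1 defines the End value as "The mean of V6 and V7 values. In case of a visit missing value, the End value will be equal to the non-missing value". The MAR paragraph of 4.1.4.1 speaks of "censoring after any protocol deviation". The estimand table in 4.5.3.1.1 gives prohibited medication a while-on-treatment strategy.

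The protocol (synopsis, and the missing-data paragraph of section 7) instead averages the last two available values, falling back on baseline. SAP 4.6, which should list changes from the protocol's statistical section, says that none apply.

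**The concern.** The imputation step is the part of the SAP that a programmer codes, and there the treatment term is absent. Imputing both arms from one pooled regression pulls imputed active and placebo patients to a common mean, which dilutes the primary estimate. With similar dropout in the two arms it also nearly reproduces J2R, so the main missing-data sensitivity analysis would no longer test anything.

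The other disagreements concern the same endpoint. Two descriptions of the MNAR option can lead to two programs. A patient who starts prohibited medication can be handled in three ways. A reader who relies on 4.6 would not learn that the missing-data rule has changed.

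Separately, neither list names a score measured after randomisation, although PDSS and CASS are collected at V3, V4 and V5. That limits what MAR can correct.

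**Working it through.** **Inputs.** 36 placebo and 72 active patients, standardised difference 0.5, R = 0.4, two-sided 0.05 (SAP 4.2). A difference of 3 UNS points (protocol synopsis, Sample Size) implies SD = 3/0.5 = 6. No dropout rate is planned. The only related count is 25 of 27 randomised patients with V6 and V7 values (protocol 7.7.2), so 2/27 = 7.4% without; arms are pooled and no reason is given. I use 7.4% and a range of 5 to 20% as assumptions.

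**The plan's own figure.** The plan gives no missing-data figure. Its power of 0.85 at 36+72 is not reproduced by a two-sided ANCOVA with R = 0.4, which gives 0.762 (0.848 one-sided). The present point does not depend on this, but the powers below should be compared only with each other. Full-data SE = 6 × √(1 - 0.4²) × √(1/36 + 1/72) = 1.12.

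**Who is imputed.** A missing V6 or V7 is replaced by the other visit, so imputation acts only on patients with neither. UNS is not scheduled between V2 and V6.

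**List B coded literally.** With a fraction d missing at random in each arm, imputed patients in both arms share one mean given baseline, so they contribute no difference and the estimate tends to (1 - d) × effect. At 7.4%: -3 × (1 - 0.074) = -2.78. In SD units, 0.5 becomes 0.475, 0.463, 0.450, 0.425 and 0.400 at 5, 7.4, 10, 15 and 20% missing.

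**J2R.** Active dropouts are given the placebo mean, so the estimate tends to (1 - d in the active arm) × effect. With equal dropout this is the same number.

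**Simulation** (proper imputation, 20 imputations, 3000 trials, 7.4% missing at random in both arms, centre not simulated):

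| Analysis | Estimate | SE | Power |
|---|---|---|---|
| Full data | -2.99 | 1.13 | 0.74 |
| Observed cases | -2.99 | 1.17 | 0.71 |
| List A (with treatment) | -2.99 | 1.18 | 0.70 |
| List B (without treatment) | -2.76 | 1.18 | 0.64 |
| J2R | -2.77 | 1.18 | 0.64 |

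List B and J2R estimates correlate 0.99. A separate simulation gave power 0.693 with treatment against 0.625 without at 7.4% missing, and 0.621 against 0.418 at 20%.

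**No on-treatment predictor, treatment included.** Here poor early responders are assumed to leave more often. The weaker setting has log-odds of dropout 1 per SD of the driver, which correlates 0.4 with the final UNS residual; the stronger has 2 and 0.6. The last column adds PDSS at V3 to V5, assumed to correlate 0.7 with the driver.

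| Dropout active/placebo | Setting | Full data | List A | J2R | List A + PDSS |
|---|---|---|---|---|---|
| 7.4/7.4% | weaker | -2.99 | -3.00 | -2.78 | -2.99 |
| 15/5% | weaker | -2.99 | -3.17 | -2.70 | -3.10 |
| 5/15% | weaker | -2.99 | -2.82 | -2.68 | -2.89 |
| 15/5% | stronger | -2.99 | -3.40 | -2.89 | -3.26 |
| 5/15% | stronger | -2.99 | -2.57 | -2.44 | -2.71 |

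The bias under unequal dropout is 0.17 to 0.42 points, or 0.15 to 0.37 SE, and none appears with equal 7.4% dropout. PDSS removes 0.07/0.18 = 39%, 0.07/0.17 = 41%, 0.14/0.41 = 34% and 0.14/0.42 = 33% of it. At a correlation of 0.4, the stronger 15/5% case moves only to -3.36, so 0.04/0.41 = 10%.

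**Prohibited medication started before V6.** Under 4.1.5.1 the patient's V6 and V7 scores enter the End value. Under the censoring sentence of 4.1.4.1 they are dropped and imputed. Under the estimand row, the last UNS at or before the medication counts; among scheduled UNS assessments that is baseline. One patient, three results.

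**The case against.** A reader might infer that the planned primary analysis omits treatment. The documents do not support that. SAP 4.1.4.1 imputes patients as members of their randomised arm, list A takes in the main model, and 4.5.3.1.2 can remove a treatment effect only if the primary model contains one. List B says what the model includes, not that it includes nothing else. All this stands. The defect is an unresolved conflict in wording, and the loss arises only if list B is followed literally. Nor is list B exactly the MNAR description in 4.5.3.1.2: list A without treatment would still keep centre.

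A reader might also infer that leaving out on-treatment scores makes the primary estimate biased. That needs unequal, response-driven dropout, which the documents do not report. Patients completing V8 can continue on open-label drug, which is a reason to stay. MAR on baseline covariates, with J2R and observed-case checks ("Using an observed Cases analysis: The same model as for the primary analysis will be performed in patients having a value of UNS"), is a coherent plan. If the active arm loses more, the primary and J2R results bracket the truth in these runs; if placebo loses more, both are too small, so the error is towards no effect. This also stands, and it makes PDSS an improvement rather than a correction.

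On prohibited medication, SAP 4.4 counts it as a deviation and 4.5.3 repeats efficacy analyses in the per-protocol set. That check helps only in part: 4.3 runs it only if that set is below 90% of the FAS, and it does not settle the primary derivation.

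The silence in 4.6 is a documentation gap. It does not show that the imputation method is wrong.

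**Conclusion.** The point holds as a conflict of specification on the primary endpoint and should be corrected. Followed literally, the imputation step dilutes the effect by about the missing fraction: from -3 to about -2.78, with simulated power 0.64 instead of 0.70, at an assumed 7.4% missing at random in each arm. The primary result then nearly equals J2R. With treatment in the model, as is almost certainly meant, this loss disappears.

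The MNAR descriptions, the handling of UNS after prohibited medication and the empty 4.6 are real inconsistencies; their numerical effect cannot be sized from the documents.

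The missing on-treatment predictor is a lesser matter. Its effect is conditional on assumed dropout patterns and is absent under equal low dropout. PDSS would recover about a third of the bias at an assumed correlation of 0.7 with what drives dropout and about a tenth at 0.4, and it does not measure the four cataplexy items of the UNS.

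**What to change.** 1. In SAP 4.1.4.1 state one MAR imputation model: treatment, centre, age, gender and the endpoint's own baseline. Change the reference from section 2.2 to 4.1.3.1. In 4.5.3.1.2 say that the MNAR option is the J2R of 4.1.4.1.

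2. As a cheap improvement, add scheduled PDSS at V3, V4 and V5 as auxiliary predictors, imputed in sequence. Name the fallback in advance: V5 only, then no post-randomisation score, if the model is unstable. With 108 patients, three correlated scores plus centre may strain it.

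3. Make the End value in 4.1.5.1, the censoring sentence in 4.1.4.1 and the prohibited-medication row in 4.5.3.1.1 give the same answer for the same patient.

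4. Record in 4.6 that multiple imputation replaces the protocol's rule. A sensitivity analysis under that old rule can be left optional: for a patient who leaves before V6 it would average the pre-treatment V2 score with a withdrawal score taken up to 5 days after the last dose.

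Items 1, 3 and 4 are mainly wording, with any derivation code following from item 3. Item 2 needs modest programming. All the variables are already collected.
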